7.11.2.4 Nosocomial Infections

A listing of nosocomial infections identified through adverse events will be produced.

7.11.2.5 Hospitalization

The duration of hospitalization (days) is defined as:

Duration of hospitalization (Days) = Date of Discharge – Date of Randomization + 1. In this context, the date of hospital discharge is the earliest hospitalization discharge date on/after the treatment completion/discontinuation date from the Treatment Disposition CRF page. Moving a patient from ICU to a regular hospital ward, would not be considered as a hospital discharge date, in this case.

However, duration of ICU (days) = Date of ICU Discharge – Date of ICU admission + 1. In this context, moving a patient from ICU to a regular hospital ward, would be considered as ICU discharge date.

For patients who died in hospital prior to Day 28, alternative methods to account for these cases, such as assigning the duration of hospitalization as 28 days, may be considered.

Duration of hospitalization will be listed for each patient, and summarized by treatment arm.

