5.2.2 Secondary Endpoints

• Change in ordinal scale.

- All cause 28-day mortality.
- Number of patients with treatment-emergent serious adverse events or clinically significant adverse drug reactions (ADRs).
- Survival time and causes of death.
- Time to improvement in oxygenation (PaO₂/FiO₂ ratio, SpO₂/FiO₂ ratio and P(A-a)O₂ gradient).
- Rate of nosocomial infection (as determined by local institution practice).
- Duration of hospitalization.
- Number of patients requiring initiation of mechanical ventilation.
- Duration of invasive and non-invasive ventilation and/or supplemental oxygen.
- Time to normalization of WBC and lymphocytes.

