7.1 General Considerations

All safety analyses will be based on Safety Population; all efficacy analyses will be based on Modified Intent-to-Treat population, unless otherwise specified. Some specific sensitivity analyses of efficacy may be based on ITT and Per Protocol populations (for primary endpoints only). See Section 7.4 below for definitions of each analysis population.

All analyses will be considered as descriptive analyses. Derivation of two-sided 95% confidence intervals and p-values will be generated where applicable.

Time to event endpoints will be defined as the start date/time to the end date/time; censoring dates will be the last date/time the patient was determined to be event-free. Kaplan Meier methods will be used for time to event endpoint analyses; a log-rank test will be performed to compare the two survival curves. Timepoints estimates and median survival will be derived from the Kaplan Meier analysis. A Cox proportional hazards model may also be used to compare the two treatment arms using a hazard ratio.

Categorical endpoints will be calculated as the percentage of patients with the event, relative to the number of patients in a given analysis population (see Section 7.4). Stratified logistic regression approaches and/or repeated measures statistical approaches may be used to compare patients on the sargramostim and control arms, in addition to Fisher's Exact or Chi² tests (as appropriate). The randomization stratification factor for the baseline SOFA score (<6 versus \geq 6) will be considered for any stratified analysis.

Continuous endpoints will be summarized by n, means, medians, minimum, maximum, and 25th and 75th percentiles. Analysis of variance, analysis of covariance, and/or repeated measures statistical approaches may be used to compare patients on the sargramostim and control arms.

In the event that the underlying assumptions and/or distributions for a given statistical method are not satisfied, alternative statistical methods will be employed.

Additional exploratory analyses may be performed to evaluate the robustness and sensitivity of the study results, including but not limited to, additional evaluation of endpoints on other

analysis populations, subgroup analyses, treatment interactions, adjusted or stratified analyses, and/or alternative statistical methods.

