7.1.5 Missing Data Handling

In general, no imputation of missing data is planned for the primary analyses. However, for purposes of any sensitivity analyses, missing data may be imputed using last-observation-carried forward, or other advanced statistical imputation methods.

For the efficacy analyses based on oxygenation parameters, up to Day 6, if the assessment on Day 6 is not available, then the last prior non-missing value, after baseline will be used. See Sections 7.1.2, 7.1.3, and 7.1.4 for algorithm on determining assessments to be used for analysis.

Imputation for P(A-a)O₂ gradient, intubation rate and ordinal scale will not be performed.

If using last observation carried forward, a missing follow-up visit value will be imputed as that patient's previously observed value.

In the absence of any other specifications, the following rule will be used for missing time-toevent data:

• Patients who are alive (not lost to follow up) and did not experience the event of interest will be censored at the date last known to be alive and to be event-free.

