7.11.1.2 Rate of Intubation, and any other Respiratory Support

Another key primary endpoint will be the rate of intubation by Day 14. That is, any occurrence of intubation (mechanical ventilation, or ECMO) at any point time in time between Days 1 and

14, will be considered to be an event. In addition, any intubation at any point during the study will be tabulated. The treatment arms will be compared using a Fisher's Exact or Chi2 test.

Furthermore, the various types of respiratory support will be summarized as specified below, including invasive ventilation (ventilator or ECMO), non-invasive ventilation by CPAP or BiPAP, high flow oxygen, low flow oxygen or no oxygen support required.

The durations of respiratory support (days) are defined as:

Duration of respiratory support

$$= \sum_{k_i=0}^{N_i} (\text{End Date/time on Day } k_i - \text{ Start Date/time on Day} k_i)/24$$

Where, N_i is the total number of available study days for any patient *i*. Respiratory support includes invasive ventilation, non-invasive ventilation and supplemental oxygen. Duration of oxygen support will be summarized by treatment arm; p-values generated from t-tests will compare the differences in the mean values between two treatment arms. These analyses will be generated for any oxygenation support, and for invasive ventilation separately.

Status of requiring respiratory support of each patient, including durations of any respiratory support (by type) will be listed.

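### Hospital stay has no value without a discharge date, and respiratory support cut off by withdrawal or death counts as a complete duration

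*SAP*

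**What the plan says.** **Hospital stay.** Section 5.2.2 lists "Duration of hospitalization" as a secondary endpoint. Section 7.11.2.5 defines it as "Duration of hospitalization (Days) = Date of Discharge – Date of Randomization + 1" and specifies that "the date of hospital discharge is the earliest hospitalization discharge date on/after the treatment completion/discontinuation date" on the Treatment Disposition page. The one special case is death in hospital before Day 28, for which alternatives "such as assigning the duration of hospitalization as 28 days, may be considered". The planned output is: "Duration of hospitalization will be listed for each patient, and summarized by treatment arm". No censoring, Kaplan-Meier analysis or test is named.

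**Respiratory support.** Section 7.11.1.2 adds up start-to-end intervals over a patient's study days, where the upper limit of the sum "is the total number of available study days for any patient". Mean durations are compared between arms by t-test, for any support and for invasive ventilation separately. The section has no rule for withdrawal or death while support is ongoing.

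**General rules.** Section 7.1.3 closes the efficacy period at the earliest of Day 90, early discontinuation from study and data cutoff. Section 7.1 says "Kaplan Meier methods will be used for time to event endpoint analyses". Section 7.1.5 says "In general, no imputation of missing data is planned for the primary analyses" and adds a default for time-to-event data where nothing else is specified: living, event-free patients are censored when last known to be so. Section 7.1 summarizes continuous endpoints by means, medians and quartiles.

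**The concern.** A duration that has not ended when observation stops is a censored time. The two formulas handle it differently, but both tend to shorten the reported duration.

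- For hospital stay, the formula returns nothing. Among patients not yet discharged when follow-up ends, whether a value is missing depends on the outcome itself: the long stays are the ones lost.
- For respiratory support, the formula returns a number that looks complete. A patient on oxygen who withdraws on Day 3 contributes about 3 days. A patient who dies on a ventilator on Day 3 also contributes about 3 days, and so looks like a favourable result.

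At stake is the comparison of two secondary endpoints. If prolonged stays, withdrawals or early deaths are more common in one arm, that arm's durations are shortened more. The trial is open-label (section 6.1), so unequal withdrawal is possible. With about 40 control patients, a few such cases can move a mean.

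**Working it through.** The SAP states no expected stay, withdrawal rate or effect size, and section 7.2 says that the sample size rests on no statistical assumption. There is no plan figure to reproduce. The check has two parts: what each rule yields for each type of patient, and illustrations on assumed inputs.

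**1. What the rules yield**

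| Patient | Stay (7.11.2.5) | Support (7.11.1.2) |
|---|---|---|
| Discharged, off support | Defined | Defined |
| Still in hospital at last follow-up or cutoff | No value | Sum to that date, taken as complete |
| Withdrawn as inpatient on support | No value | Sum to withdrawal, taken as complete |
| Died in hospital before Day 28 | Optional rule, 28 days as an example | Sum to death, taken as complete |
| Died in hospital on or after Day 28 | No rule | Sum to death, taken as complete |

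**2. Hospital stay, loss through end of follow-up only**

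Assumed: lognormal stay, median 10 days, log-SD σ = 0.8. True mean = 10 × exp(0.8²/2) = 10 × exp(0.32) = 13.77 days.

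If discharge dates are known only to day T, let z = ln(T/10)/σ. The share without a date is 1 − Φ(z). The mean among those with a date is 13.77 × Φ(z − σ)/Φ(z).

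| T | z | Share without a date | Mean reported | Understatement |
|---|---|---|---|---|
| 28 | 1.287 | 9.9% | 10.50 | 3.3 days |
| 58 | 2.197 | 1.4% | 12.83 | 0.9 days |
| 90 | 2.747 | 0.3% | 13.46 | 0.3 days |

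At T = 90, 0.3% of 120 is about 0.4 patients. The median moves less: from 10 to 9.86 at Day 58 and to 9.97 at Day 90.

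**3. Hospital stay, any reason for a missing date**

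Assumed: discharged patients average 12 days, and a share p has no discharge date but stays to Day 28. The discharged-only mean is 12.0 whatever p is. Counting everyone to Day 28 gives 12(1 − p) + 28p: 12.8 at 5%, 13.6 at 10%, 14.4 at 15% and 15.2 at 20%. The understatement is 0.8 to 3.2 days.

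If p were 5% in one arm and 15% in the other, the discharged-only means would be equal, while the means to Day 28 would differ by 14.4 − 12.8 = 1.6 days.

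**4. Respiratory support**

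Assumed: 10 days on average in patients followed, and a share p withdrawn on Day 5 who would have stayed on support to Day 28. The SAP's sum gives 10(1 − p) + 5p; full accrual gives 10(1 − p) + 28p; the gap is 23p.

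| p | SAP sum | To Day 28 | Gap |
|---|---|---|---|
| 5% | 9.75 | 10.9 | 1.15 |
| 10% | 9.5 | 11.8 | 2.3 |
| 20% | 9.0 | 13.6 | 4.6 |

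Support to Day 28 is the extreme case for such patients, so these gaps are upper limits for each p.

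**The case against.** The strongest reply is that the SAP nowhere says these patients are dropped. Section 7.1 describes time-to-event endpoints broadly, as a start to an end date, and section 7.1.5 supplies a censoring default. Randomization to discharge could be read as falling under both. The no-imputation sentence in 7.1.5 concerns the primary analyses, whereas these endpoints are secondary.

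This stands in part: exclusion is an inference. It does not remove the problem. Both endpoints are named and defined as durations, each with its own formula, and neither section invokes the default. Section 7.11.2.2, by contrast, sets out Kaplan-Meier, censoring and a Cox model for mortality. For support, a t-test on means is named, which cannot accommodate censoring. Followed as written, the plan produces a discharged-only summary of stay and a truncated sum of support.

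A second reply concerns size. A reader might infer that a bias of about 3 days is to be expected. The SAP does not support that: the figure requires discharge dates to stop at Day 28, whereas the efficacy period runs to Day 90, where the same assumption gives 0.3 days. Medians are also reported and move little.

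A third concerns direction between arms. A reader might infer that one arm is favoured. Nothing in the SAP shows this; it depends on losses differing by arm, which cannot be known in advance. No test is planned for hospital stay, and sections 7.1 and 7.2 call all analyses descriptive. These replies limit the importance of the point but leave the gap open.

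**Conclusion.** The point holds as a moderate defect in two secondary endpoints. Section 7.11.2.5 gives no stay to patients without a discharge date and handles in-hospital death only optionally, and only before Day 28. Section 7.11.1.2 treats support cut off by withdrawal or death as complete. Both tend to understate duration.

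The size cannot be determined from the SAP. End-of-follow-up loss alone is likely to be minor if discharge dates are collected to Day 90. Withdrawal, an early cutoff and death matter more, and the SAP gives no rates for them. The illustrations rest wholly on assumed stay distributions and loss shares. Those for withdrawal also assume that the patients lost would have stayed in hospital or on support to Day 28. Bias in the arm comparison is conditional on unequal losses.

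The primary endpoints, the A-a gradient and intubation by Day 14, are not touched by this point.

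**What to change.** **Section 7.11.2.5.** Analyse time from randomization to hospital discharge in all MITT patients. Censor patients still in hospital or withdrawn at the last date they were known to be inpatients. Treat in-hospital death as a competing event, whenever it occurs, and report the cumulative incidence of discharge by Days 14 and 28 in each arm. Death should be neither a discharge nor ordinary censoring: censoring deaths in a Kaplan-Meier analysis overstates the proportion discharged and can favour an arm with more early deaths.

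**Section 7.11.1.2.** Replace the t-test on accrued days with days alive and free of respiratory support to Day 28, and separately free of invasive ventilation. Assign zero to deaths and compare arms by a rank-based test. State a sensitivity analysis for patients who withdraw while on support. Time to end of support would not be a suitable substitute, because the SAP's quantity is cumulative and support can stop and restart.

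**Cost.** Small SAP and programming changes, with no new patients. The cumulative incidence analysis goes beyond the Kaplan-Meier output already planned. The support summary becomes a composite with death, so it no longer describes time on support alone. The existing durations can still be listed descriptively alongside.

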7.1.1 Study Day

Study day will be calculated as follows:

- For the sargramostim arm: Assessments/events prior to the first sargramostim dose date, study day will be the assessment date minus the first dose date. The end of treatment is the date/time of the last administered dose of sargramostim.
- For the control arm, the randomization date will be used as the first dose date. The treatment completion or discontinuation date/time from the treatment disposition CRF page will be considered the end of treatment for the SOC arm.
- Assessments/events on or after the first dose date, study day will be the assessment date minus the first dose date plus one.
- The duration of SOC (for both treatment arms) will be based on the start date of randomization, and the end date as latest of 1) any concomitant medication end date with indication "COVID-19", or 2) any end date of procedure with indication "COVID-19", or 3) any end date of transfusion, ventilation or supplemental oxygen.

For assessments captured as an unscheduled visit, if the date of assessment is the same as a date of another visit (e.g., Day 6, Day 14, Day 28, Day 58, Day 90), then the visit label for the unscheduled assessment can be re-assigned to the appropriate visit label (e.g., Day 6, Day 14, Day 28, Day 28, Day 58, Day 90). Other appropriate data handling approaches may be used to ensure data is analyzed in the appropriate timepoint analysis.

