7.10 Extend of Exposure and Treatment Compliance

Study days, including first and last dose, to enable deviation of treatment durations for both treatment arms are defined in Section 7.1.1.

Treatment duration and treatment compliance will be summarized for the Safety Population. For each patient, the treatment duration is defined as the number of days from the first treatment date to the last treatment date, and can be calculated as:

Treatment Duration (Days) = (Date and Time of Last Treatment – Date and Time of First Treatment)/24 +1.

The result of treatment duration will be rounded to the nearest integer. For example, if the calculation results in 5.4 days, then the final result of treatment duration will be 5 days.

See Section 7.1.4 for handling missing treatment times. Otherwise, if time of the last treatment is not available, the end time of the treatment duration will be imputed using the earliest of 1) End time of treatment Day 5; or 2) Time of patient's early discontinuation from the treatment or from the study (where available). Treatment duration will be calculated for both treatment arms, and will include any treatment, sargramostim, and standard of care durations.

For each patient who received sargramostim, the treatment compliance is defined as the actual treatment received as percentage of the planned treatment (K days). It can be calculated as:

Treatment Compliance = 100*(Treatment Duration– Number of Days without Study Treatment)/K

In this study, the prespecified treatment duration of sargramostim is 5 days (K=5).. For discontinued patients, K would be equal to the number of days from the date the sargramostim study drug is first received to the date of early discontinuation.

K can be smaller than 5 1) if the end of the treatment/early discontinuation of treatment before Day 5; 2) if the patient has not completed 5 days of sargramostim treatment and has not discontinued treatment/study early by the time of the data cut.

Since there is no planned or prespecified treatment duration for the standard of care therapies, compliance with standard of care cannot be determined or summarized.

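### Hospital discharge is tied to the recorded treatment end date, so a patient in either arm who goes home before that date loses the true length of stay

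*SAP*

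**What the plan says.** SAP section 7.11.2.5 gives the formula "Duration of hospitalization (Days) = Date of Discharge – Date of Randomization + 1". It then states that "the date of hospital discharge is the earliest hospitalization discharge date on/after the treatment completion/discontinuation date" on the Treatment Disposition CRF page. The wording is the same for both arms. A move from ICU to a ward is not a hospital discharge. In-hospital deaths before Day 28 have a separate, optional provision. Nothing is said about a patient whose discharge comes before the Treatment Disposition date, or about readmissions.

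Two other sections bear on what that date means:

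- Section 7.1.1 says of the completion or discontinuation date that, taken "from the treatment disposition CRF page will be considered the end of treatment for the SOC arm". For the sargramostim arm it says: "The end of treatment is the date/time of the last administered dose of sargramostim".
- Section 7.10 fixes the sargramostim course at 5 days. It explains why control compliance is not summarized: "Since there is no planned or prespecified treatment duration for the standard of care therapies".

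Section 7.11.1 expects that some patients will be discharged before Day 6, since it provides for the blood gas to be taken on the day of discharge if that is earlier.

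**The concern.** The duration runs from randomization to discharge, so the endpoint does not need a treatment end date. Adding one as a lower bound means that a real discharge can be passed over. The patients exposed are those who leave hospital soonest. Losing or lengthening their stays distorts an arm's summary at its short end.

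The condition could also act unequally. A sargramostim course has a planned end at 5 days, whereas standard of care has none, and in this open-label trial (section 6.1) the control end date is whatever the site records. Duration of hospitalization is listed in section 5.2.2 and summarized by arm. About 40 controls are planned, so a few affected patients could move a mean visibly.

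**Working it through.** The SAP gives no expected length of stay and no power calculation, so there is no stated figure to reproduce. The check applies the section 7.11.2.5 rule literally:

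duration = min(discharge dates ≥ Treatment Disposition date) − randomization date + 1

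**Example timelines.** Randomization is on Day 1; all dates are assumed.

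| Arm | Discharge | Disposition date | True stay | Stay under the rule |
|---|---|---|---|---|
| Sargramostim | Day 8 | Day 5 | 8 | 8 |
| Sargramostim | Day 4 | Day 4 | 4 | 4 |
| Sargramostim | Day 4 | Day 5 | 4 | none |
| Control | Day 8 | Day 5 | 8 | 8 |
| Control | Day 8 | Day 8 | 8 | 8 |
| Control | Day 8 | Day 10 | 8 | none |
| Control | Day 8, readmission ends Day 25 | Day 10 | 8 | 25 |

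The rule is right whenever the disposition date is on or before discharge. It fails in either arm when the disposition date is later.

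**Illustrative size within one arm.** The arm size of 40 controls is from section 7.2. The rest is assumed: a fraction f of the arm is affected, affected patients truly stay 7 days, the others average 12, and a readmission ends on Day 25.

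- True mean = 7f + 12(1 − f).
- If affected patients drop out of the summary, the mean becomes 12, a shift of f × (12 − 7) = 5f.
- If their stays are replaced by the readmission discharge, the shift is f × (25 − 7) = 18f.

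| f | Controls affected | True mean | Shift if missing | Shift if replaced |
|---|---|---|---|---|
| 5% | 2 of 40 | 11.75 | 0.25 days | 0.9 days |
| 10% | 4 of 40 | 11.50 | 0.5 days | 1.8 days |
| 25% | 10 of 40 | 10.75 | 1.25 days | 4.5 days |

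The last column requires every affected patient to be readmitted, so it is an upper illustration.

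**Between arms.** With the same assumed stays in both arms, the control-minus-sargramostim difference shifts by 5 × (f in controls − f in sargramostim), or by 18 times that gap if stays are replaced. Equal fractions cancel. The sign therefore depends on two fractions that the SAP does not give.

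**The case against.** A reader might infer that the loss falls mainly on controls and so biases the endpoint in favour of sargramostim. The SAP does not support that as a statement of fact:

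- Section 7.11.2.5 uses one CRF date for both arms. The last-dose definition in section 7.1.1 is not invoked there, so the rule itself contains no difference between arms.
- Section 7.1.1 derives a separate, longer duration of standard of care from the latest COVID-19 medication, procedure, transfusion, ventilation or oxygen end date. The discharge rule does not use it.
- Section 6.4.3 heads the treatment period as Days 1-5 without distinguishing arms. Section 7.1.4 uses the control completion date, or the Day 6 visit if later, to place the Day 6 evaluation. Both suggest a control date close to Day 5 or 6, though neither caps it.
- If sites enter the discharge day or an earlier day as treatment completion, nothing is lost. The CRF guidelines may settle this; the SAP does not.

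It can also be said that the endpoint is secondary, that all analyses are descriptive (section 7.1), that section 7.11.2.5 names no test, and that the patient listing would expose missing or odd durations.

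These points remove any firm claim about direction or size and limit the weight of the issue. They do not supply a rule for the patient discharged before the disposition date. A listing may reveal the gap, but only after the data are in, when a choice about those patients would no longer be prespecified.

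**Conclusion.** The point holds as a defect in the stated rule, in both arms. Any discharge before the recorded treatment end is passed over without a fallback. A replaced stay is always longer than the true one, and a dropped stay raises the arm mean if it was below average.

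A higher frequency in controls is plausible, because their recorded end of treatment relates to therapy with no planned duration. It is not established. It rests on sites recording completion after the patient has gone home, and doing so more often for controls. The number of patients affected, and the size and direction of any bias between arms, cannot be computed from the SAP; the shifts of 0.25 to 4.5 days shown above are illustrations on assumed inputs. The issue is worth correcting because the repair is cheap.

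**What to change.** In section 7.11.2.5, define the discharge date in both arms as the first discharge from hospital on or after randomization, and delete the reference to the treatment completion or discontinuation date. State also that:

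- ICU-to-ward moves (as already written) and transfers between hospitals are not discharges;
- a readmission does not replace the index discharge;
- in-hospital deaths stay under the section's existing separate provision.

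Patients whose first discharge from hospital after randomization is already selected keep the same duration. The cost is one or two SAP sentences and a check of discharge records for transfers, which the treatment-end condition may at present screen out by accident. Discharge and randomization dates are already needed for the existing formula.
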